### 6.2 A091105-HO1 (QOL) data submission

QOL booklet ordering instructions can be found in [Appendix II](#). For patients who consent to model consent question #1, the assessments in the table below are to be completed at the following timepoints:

| Assessment                      | Within 28 days prior to randomization | Within 28 days prior to treatment | Weeks 4, 8, 12, 16, 20, 24, 28, and 32 of treatment (+/- 3 days)
(i.e. Cycles 1-8, Days 22-28) | End of randomized treatment |
|---------------------------------|---------------------------------------|-----------------------------------|---------------------------------------------------------------------------------------------------|-----------------------------|
| Brief Pain Inventory Short Form | X                                     |                                   | X                                                                                                 | X                           |
| PRO-CTCAE                       | X                                     |                                   | X                                                                                                 | X                           |
| Single-item overall LASA        | X                                     |                                   | X                                                                                                 | X                           |
| Pain Medication Diary           |                                       | X*                                | X                                                                                                 | X                           |

\* Daily reporting for 7 consecutive days via paper diary prior to treatment. Pain medication diary is not found in QOL booklet.

The Brief Pain Inventory Short Form, PRO-CTCAE and Single-item overall LASA are all contained with the QOL questionnaire booklets (see [Appendix II](#)). **Samples of QOL questionnaires found in Appendix II of the protocol document are for reference and IRB submission only. They are not to be used for patient completion.**

The pain medication diary is not part of the QOL Booklet and must be printed. The pain medication diary should be completed during treatment weeks 4, 8, 12, 16, 20, 24, 28, and

32 weeks. Therefore, since a cycle is 28 days, the pain medication diary should be completed the last week of each cycle.

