- \* Pre-registration labs may be used for day 1 of cycle 1 tests if obtained within 28 days prior to day 1 of Cycle 1.
- \*\* For patients discontinuing treatment for reasons other than progressive disease (PD) and prior to 1 year post-randomization, Clinical Follow-up continues at least every 8 weeks after discontinuing treatment until the earliest PD or until 1 year after randomization. Patients on the placebo arm may cross over to the sorafenib arm upon PD, and continue in Clinical Follow-Up. Treatment with sorafenib after crossover must begin within 28 days following documentation of progression.
- \*\*\* After progression on sorafenib, patient will be followed per. [Section 14.1](#)
- † For patients who consent to A091105-ST1. Not required for patients who have crossed over to sorafenib.
- 1 To be performed only for patients with palpable disease. Submit measurements in cm with two dimensions.
- 2 To be completed within 21 days prior to registration, see Appendix I.
- 3 Within 28 days prior to randomization, every 4 weeks up to Week 32 while on randomized treatment, and at the end of randomized treatment; see [Section 6.2](#). These items are not required after patients have crossed over to sorafenib.
- 4 For women of child bearing potential. To be obtained within 3 days prior to day 1 of Cycle 1, **and** after crossover, ≤ 7 days prior to starting treatment with sorafenib.
- 5 Required for all patients registered to A091105 and will be used for confirmation of diagnosis as described in [Section 6.3.1](#). For patients who consent to A091105-ST1, this tissue block will also be used for study described in [Section 10.3](#).

- 6 Must be completed within 28 days of registration. Patients who consent to A091105-HO1 will meet this requirement by answering question #1 on baseline QOL assessment (see [Appendix II](#)). For patients who do not consent to A091105-HO1, see [Appendix V](#).
- 7 All MRI images are to be submitted to the Alliance ICL per [Section 6.4](#) and will be analyzed as described in [Section 10.1](#)

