• **Pain Medication Diary:** Daily reporting for 7 consecutive days via paper diary prior to randomization, every 4 weeks through Week 32 while on randomized treatment, and at end of randomized treatment. This pain medication diary will be used to quantify opioid narcotic use for computing pain palliation and pain progression.

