### 10.2.3 Specific hypotheses

Our primary hypothesis is that pain palliation will be improved on the sorafenib arm as compared to the placebo arm as suggested by the retrospective review by Gounder et al. Our secondary hypothesis is that time to pain progression will be extended on the sorafenib arm as compared to the placebo arm, based on our hypothesis that sorafenib will prolong progression-free survival. To understand the impact of the hypothesized pain improvement associated with sorafenib on patients, pain interference on general activity and sleep will also be compared between arms, where we expect interference in both domains to be improved on the sorafenib arm as compared to the placebo arm. In terms of patient-reported adverse events, we hypothesize that pain and insomnia will be improved on the sorfenib arm as compared to the placebo arm; and that fatigue, gastrointestinal toxicity (constipation, nausea, vomiting, diarrhea, decreased appetite, and mouth or throat sores) and skin toxicity (rash, hand-foot syndrome) will be negatively impacted on the sorafenib arm as compared

to the placebo arm given the adverse event profile of sorafenib in other patient populations and based on the adverse events reported in the retrospective review by Gounder et al. Lastly, given the possibility of improved pain and insomnia at the cost of increased treatment toxicity, we will compare overall quality of life between arms and hypothesize that quality of life will be improved on the sorafenib arm as compared to the placebo arm (i.e., that larger improvement in pain will offset the added toxicity of sorafenib treatment).

The Alliance Statistics and Data Center A091105-HO1 Statistician collaborate with the A091105 Statistician to prepare analysis datasets in conjunction with clinical/outcome data. Analyses will be conducted by the A091105-HO1 Statistician, using the analysis datasets used for the analysis of the clinical endpoints to ensure consistent data is reported for the primary and secondary endpoints (e.g. data associated with censoring, proper inclusion of crossover data, and data to be excluded in cases of consent withdrawals for follow-up and correlative studies).

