#### 15.3.2 Statistical design- A091105-H01, QOL study

Pain palliation will be defined at each time point as  $\geq 30\%$  decrease from baseline in the worst pain intensity score (BPI-SF "worst pain" item), with neither a concomitant  $\geq 30\%$  increase in average daily use of any opioid narcotic, nor addition of any new opioid narcotic, relative to baseline.

A patient must meet the criteria for pain palliation at both Week 8 and Week 12 to be considered a responder for the primary endpoint. The primary statistical analysis will include all eligible and consented patients who provide baseline pain and pain medication data, have a baseline pain level greater than or equal to 3, and who initiate treatment. Any patient who does not provide pain and pain medication data at Week 8 and Week 12 will be considered a non-responder (i.e., a "failure" for the endpoint but will be included in the denominator).

Pain progression at a given time point is defined as a  $\geq 30\%$  increase compared with baseline in the worst pain intensity score (BPI-SF "worst pain" item) or either a  $\geq 30\%$  increase in the average daily use of any type of opioid narcotic or the addition of a new opioid narcotic compared with baseline. Time to pain progression is defined as the date of randomization to the earliest date that pain progression is observed. Patients not reporting pain progression will be censored at their date of last pain and pain medication data reporting. Time to pain palliation is defined as the date of randomization to the earliest date that confirmed pain palliation is observed. Duration of pain palliation is defined for all patients who experience confirmed pain palliation and is the time from the earliest date that confirmed pain palliation is observed to the earliest date that pain progression is observed. Patients not reporting pain progression will be censored at their date of last pain and pain medication data reporting.

For the primary analysis, the rate of pain palliation at Week 8 confirmed as Week 12 will be compared between arms using a two-sided  $\alpha=0.05$  chi-squared tests at the time of the final analysis.

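### After Week 32 pain progression can be dated only when randomised treatment ends, so the time-to-pain-progression comparison can modestly favour sorafenib even if pain is the same in both arms

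*Combined protocol and SAP*

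**What the plan says.** Section 15.3.2 defines the event date: "Time to pain progression is defined as the date of randomization to the earliest date that pain progression is observed". It censors the rest: "Patients not reporting pain progression will be censored at their date of last pain and pain medication data reporting". Arms are compared by Kaplan-Meier estimates and a log-rank test, with p below 0.05 called significant. Duration of pain palliation ends at the same pain-progression date.

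The study calendar (Section 7.0, footnote 3) collects the pain items "Within 28 days prior to randomization, every 4 weeks up to Week 32 while on randomized treatment, and at the end of randomized treatment". Section 10.2.2 gives the pain medication diary the same schedule: "every 4 weeks through Week 32 while on randomized treatment, and at end of randomized treatment". The table in Section 6.2 agrees. After crossover there is nothing: "These items are not required after patients have crossed over to sorafenib".

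Randomised treatment has no fixed length. Sections 8.3 and 14.1 continue it until PD or unacceptable toxicity. Section 15.1.1 assumes median PFS of 6 months on placebo and 15 months on sorafenib.

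Section 10.2.3 states the hypothesis that "time to pain progression will be extended on the sorafenib arm as compared to the placebo arm", and bases it on the expected PFS benefit. Section 10.2.1 lists the endpoint as secondary within HO1, while Section 15.3.2 analyses it among exploratory hypotheses. No section gives a Week 32 cut-off, an interval-censoring rule or later pain visits. The missing-data paragraph deals with missing reports and does not address a gap in the schedule itself.

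**The concern.** Up to Week 32 both arms are observed every 4 weeks and detection is even-handed. After Week 32 the only remaining observation is triggered by the end of randomised treatment, and the trial is designed to move that time by arm.

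Take two patients whose pain worsens at Week 36. If treatment ends at Week 40 for one and Week 80 for the other, their recorded times to pain progression are 40 and 80 weeks. If the later treatment end is more common on sorafenib, the log-rank test sees a delay in pain progression that is only a delay in looking.

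Because the hypothesis is itself derived from the PFS hypothesis, a result of this kind would look like confirmation. At stake is the interpretation of one patient-reported endpoint, and of duration of pain palliation, which uses the same date.

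**Working it through.** **Inputs from the documents.** Last scheduled on-treatment pain visit: Week 32, or 32 × 7 / 30.44 = 7.36 months (Sections 6.2 and 7.0). Scans every 8 weeks (Section 7.0, footnote A). Median PFS 6 versus 15 months, HR 0.40; 25 placebo and 50 sorafenib patients; 4 patients per month; at least 12 months' follow-up; final analysis at 52 events or 3 years (Section 15.1.1).

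**Assumptions, not in the documents.** Exponential time to pain progression, identical in both arms, persistent once reached and independent of PD. True median 26 to 78 weeks, with 24 months as a further case. The log-rank test is taken as two-sided at 0.05, so 2.5% false claims for sorafenib are expected.

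**The plan's own figure.** There is none for this endpoint. The PFS power that supplies the treatment-duration gap is stated as 90%. Schoenfeld's formula gives z = 0.916 × √(52 × 1/3 × 2/3) − 1.96 = 1.155, or 87.6%. Simulating the log-rank test at the 52nd event with one-sided 0.0255 gives 89.0%. The PFS assumptions are coherent and can be used.

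**Step 1: who enters the gap.** Progression-free, and so taken as still on treatment, at Week 32:
- sorafenib: 0.5^(7.36/15) = 0.71
- placebo: 0.5^(7.36/6) = 0.43

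**Step 2: what is measured after Week 32.** Observed event hazard = (hazard of ending treatment) × (probability that pain has already worsened). With the same pain course the second factor is about equal between arms, so the ratio tends to 6/15 = 0.40. Simulation gives 0.40 to 0.43 with complete follow-up, 0.57 to 0.60 at 3 years and 0.77 to 0.81 at 12 months. The weakening comes from the censoring rule. At 3 years 0.5^(36/15) = 19% of sorafenib and 0.5^(36/6) = 1.6% of placebo patients are still on treatment. Without an earlier pain event they are censored at Week 32 and add nothing to the late part.

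**Step 3: how much of the endpoint is exposed.** Probability of pain progression by Week 32 is 1 − 0.5^(32/m):
- m = 26 weeks: 0.57
- m = 52 weeks: 0.35
- m = 78 weeks: 0.25

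With m = 26 the median falls before Week 32 and cannot be distorted. For true medians of 6 to 24 months, late events are about 12 to 47% of all observed events with up to 3 years' follow-up.

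**Step 4: whole endpoint, identical pain in both arms, 25:50.**

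| Follow-up | True median | HR | KM median, sorafenib vs placebo | False claims for sorafenib |
|---|---|---|---|---|
| 3 years per patient | 26 weeks | 0.94 | 28 vs 28 weeks | 3.7% |
| 3 years per patient | 52 weeks | about 0.91 | 88 vs 72 weeks | 5.3% |
| 3 years per patient | 78 weeks | 0.88 | – | 4.8% |
| 3 years after last entry | 6 months | 0.90 | 6.4 vs 6.4 months | 4.9% |
| 3 years after last entry | 12 months | 0.85 | 22.1 vs 16.6 months | 6.2% |
| 3 years after last entry | 24 months | 0.86 | 31.3 vs 25.8 months | 6.0% |
| 12 months | 6 to 24 months | 0.95–0.99 | – | – |

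**Step 5: does the mechanism behave as claimed?**
- Equal PFS (6 months) in both arms: HR 1.01, so the bias comes from the difference in treatment end.
- Transient worsening (3 to 10% chance per visit): about 0.94 to 0.96.
- An assumed 25%, 50% or 75% of pain progressions themselves ending treatment: 0.94, 0.95 and 1.01.
- An assumed 40% per year non-PD discontinuation on sorafenib against 5% on placebo: about 0.98.
- All worsening between months 8 and 12: 0.56 to 0.57, with false claims of 26% (51 patients) to 36% (75 patients).

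**Step 6: after the change.** Censoring everyone at Week 32 gives HR 0.98 to 1.03 and false claims for sorafenib of 2.6 to 3.6%.

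**The case against.** The strongest reply is that pain and treatment end are not independent. Section 13.4.5 counts worsening tumour-related symptoms, when they force discontinuation, as PD, and Section 11.2.6 unblinds on radiographic or clinical progression. Patients on initial treatment are seen every cycle. Persistent tumour pain can therefore itself bring about the end-of-treatment report, and if half or more of pain progressions did so the bias would nearly vanish. This stands as a limit on size. The documents do not say how often it would happen, and it does not supply a rule for the rest.

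The endpoint also sits in an optional substudy, is called exploratory in Section 15.3.2, and uses a worst-pain item that covers only the last 24 hours (Appendix V). That lowers the stakes.

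A reader might infer something stronger, and three such readings fail:
- **The whole endpoint is a disguised time to PD.** Only the part after Week 32 is tied to treatment end; earlier events are seen every 4 weeks.
- **Medians are inflated in both arms, always more on sorafenib.** With a true median of 26 weeks both arms show 28 weeks.
- **The distortion is as large as 104 versus 72 weeks, HR about 0.79 and 7.6% false claims.** Those figures arise only if every patient still on treatment at Week 156 gives a pain report then. The protocol schedules none; such patients are censored at Week 32.

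**Conclusion.** The gap is explicit in the schedule, and Section 15.3.2 has no rule for it. Under the design's own PFS assumptions the direction is towards sorafenib. The size is modest: HR about 0.85 to 0.94 and false claims of about 4 to 6% at 3 years' follow-up, for persistent pain progression independent of PD with a true median of 26 to 78 weeks. It is slight at 12 months, if worsening is transient, or if worsening often ends treatment. It is larger if worsening clusters soon after Week 32. The pain rate is undocumented, so the direction is better supported than any single figure.

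The HO1 primary endpoint (palliation at Weeks 8 and 12), PFS and all pain events up to Week 32 are untouched. Duration of pain palliation shares the problem. This is a cheap improvement to a subsidiary analysis and no threat to the trial's main conclusion.

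**What to change.** In Section 15.3.2:
- Administratively censor the between-arm log-rank test of time to pain progression, and of duration of pain palliation, at the Week 32 assessment plus its window. Let an end-of-treatment report count, as event or censoring date, only if it falls by then.
- Report the Week 32 pain-progression-free rate per arm.
- Present the full-follow-up analysis with later end-of-treatment reports as descriptive or supportive only, or analyse it as interval-censored.

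The cost is wording; no new data are needed. The downside is that pain progressions first seen after Week 32 leave the test, and a median may not be estimable. An interval-censored supportive analysis keeps the late information for readers who want it.

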For the exploratory hypotheses, median time to pain palliation, duration of response, and time to pain progression will be estimated for each arm using Kaplan-Meier estimates and will be compared between arms using a log-rank test. All other items/questionnaires will be scored according to published scoring guidelines and statistical analysis will include all eligible and consented patients who provide data for the given outcome and who initiate treatment (i.e., the requirement for baseline pain to be  $\geq 3$  is not in effect for the other outcomes). Descriptive statistics will include means, standard deviations, medians, and ranges for each continuous or ordinal scale/subscale/item by group at each time point. Descriptive graphical techniques will include mean plots by group for each continuous or

ordinal scale/subscale/item. Relative frequencies of responses for each ordinal item will also be generated at each time point by group.

Each patient-reported outcome will be compared between arms at each time point using two-sample t-tests followed by analysis of covariance adjusting for the baseline value at each time point. Finally, a linear mixed-effects model with random intercepts and slopes will also be used to compare each continuous/ordinal patient-reported outcome over time between arms. In these linear mixed-effects models, the post-baseline score is the modeled outcome and the predictors are the baseline score of the given patient-reported outcome, arm, time (treated as a continuous variable and measured at the planned week of assessment), and treatment-by-time interaction.

Missing data will be handled in a number of ways. Baseline patient/disease characteristics will be compared between patients who provide data and patients who have missing data for each endpoint. We will also graphically explore patterns of missing data. All analyses will be completed using all available data, followed by analyses completed using imputed data using the arm minimum followed by the arm maximum. Lastly, we will employ pattern mixture models for longitudinal analyses. Output from all analyses will be compared to assess the degree to which missing data impacts study results.

For all statistical analyses, p-values <0.05 will be considered statistically significant. For interpreting the clinical significance of effects, 0.2, 0.5, and 0.8 SD effects will be considered as small, moderate, and large based on Cohen throughout.

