**Power:** We anticipate ~70% of eligible patients who initiate treatment will be evaluable for the primary analysis of this companion study. With 51 patients contributing data for the primary analysis, the primary analysis has 80% power to detect a 40% difference in the rate of pain palliation at Week 8 confirmed at Week 12 between arms (50% pain palliation in the sorafenib arm versus 10% in the placebo arm) using a two-sided alpha=0.05 chi-squared test. Power for a 45% difference (55% pain palliation in the sorafenib arm versus 10% in the placebo arm) is 87%. These power calculations assume 2:1 randomization. This power calculation conservatively assumes that 10% of patients in the placebo arm will experience a “placebo effect” such that patients report improvement in pain despite being treated with a placebo.

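### In the quality-of-life sub-study, the arm-minimum and arm-maximum imputations shift both arms the same way, so they do not bound the arm difference, and no tipping-point analysis is planned for the by-visit comparisons

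*Combined protocol and SAP*

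**What the plan says.** Section 15.3.2 compares each patient-reported outcome between arms at each time point by t-test and then by ANCOVA adjusted for baseline. A linear mixed model over time follows.

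For missing data, the section first compares the baseline characteristics of patients with and without data and graphs the missingness patterns. Then: "All analyses will be completed using all available data", "followed by analyses completed using imputed data using the arm minimum followed by the arm maximum". It adds: "Lastly, we will employ pattern mixture models for longitudinal analyses". The purpose is stated: "Output from all analyses will be compared to assess the degree to which missing data impacts study results".

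The primary pain-palliation endpoint has its own rule: "Any patient who does not provide pain and pain medication data at Week 8 and Week 12 will be considered a non-responder".

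Under Section 7.0, footnote 3, forms are collected "every 4 weeks up to Week 32 while on randomized treatment" and once more when randomized treatment ends. They are not required after crossover.

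Section 15.3.2 does not mention a run that pairs one arm's minimum with the other arm's maximum, an arm-specific shift, or a tipping point. It also does not say whether the arm minimum is the lowest observed score or the bottom of the scale, or whether it is taken per visit.

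**The concern.** The question for a comparison between arms is how different the missing outcomes would have to be, in one arm relative to the other, before the conclusion changed. Filling both arms with low values and then both with high values does not ask this. The imputed contributions cancel to the extent that the arms have similar missing fractions and similar extremes.

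In the balanced case the two runs agree exactly, as a matter of algebra, whatever the missing patients experienced. A reader told that the outputs are compared to judge the effect of missing data could take that agreement as evidence of robustness.

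Missingness here is unlikely to be unrelated to outcome, because scheduled collection stops with randomized treatment and the design expects placebo patients to progress sooner. Section 10.2 gives patient-reported outcomes secondary-endpoint standing, so the by-visit results are likely to be reported and read.

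**Working it through.** **The plan's own figure.** Section 15.3.2 gives no number for the imputation check. The only figure there that can be reproduced is the palliation power: "With 51 patients contributing data for the primary analysis, the primary analysis has 80% power to detect a 40% difference", "using a two-sided alpha=0.05 chi-squared test". With 34 and 17 patients and rates of 50% and 10%, the pooled rate is (17 + 1.7)/51 = 0.367. The pooled standard error is √[0.367 × 0.633 × (1/34 + 1/17)] = 0.143. Power is Φ(0.40/0.143 − 1.96) = 79.8%. For 55% against 10% the same formula gives 87.1%. Both match the stated 80% and 87%, so the power statement is not in question.

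**Formula for the check.** Let m be the missing fraction, o the observed mean and i the imputed value, for sorafenib (S) and placebo (P):

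D = [(1 − mS)·oS + mS·iS] − [(1 − mP)·oP + mP·iP]

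With common extremes L and U:
- The minimum run sets iS = iP = L and the maximum run sets iS = iP = U. The two results differ by |mS − mP| × (U − L).
- The possible range of D runs from (iS = L, iP = U) to (iS = U, iP = L). Its width is (mS + mP) × (U − L).

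The planned pair therefore responds to the difference of the missing fractions, and the true uncertainty to their sum.

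**Equal missingness.** Section 10.2.2 gives the overall LASA item a 0-10 scale. Observed means of 6.5 and 5.5 and the missing fractions are assumptions. At 30% missing per arm:
- Minimum run: 0.7 × 6.5 − 0.7 × 5.5 = 4.55 − 3.85 = +0.70
- Maximum run: (4.55 + 3.00) − (3.85 + 3.00) = +0.70
- Possible range: 4.55 − 6.85 = −2.30 to 7.55 − 3.85 = +3.70

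**Other missing fractions and ranges, same assumed means.**

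| Missing S / P | Range S / P | Minimum run | Maximum run | Crossed pairings |
|---|---|---|---|---|
| 10% / 10% | 0-10 / 0-10 | +0.9 | +0.9 | −0.1 to +1.9 |
| 20% / 20% | 0-10 / 0-10 | +0.8 | +0.8 | −1.2 to +2.8 |
| 30% / 30% | 0-10 / 0-10 | +0.7 | +0.7 | −2.3 to +3.7 |
| 20% / 40% | 0-10 / 0-10 | +1.9 | −0.1 | −2.1 to +3.9 |
| 40% / 20% | 0-10 / 0-10 | −0.5 | +1.5 | −2.5 to +3.5 |
| 30% / 30% | 2-10 / 0-9 | +1.3 | +1.0 | −1.4 to +3.7 |

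In the last row each arm is filled with its own observed extremes. The minimum run then exceeds the observed difference of 1.0 only because the two arms' extremes differ.

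**Week 32 under the design PFS.** Section 15.1.1 assumes medians of 15 and 6 months. Week 32 is 7.36 months. Exponential PFS leaves 2^(−7.36/15) = 0.712 and 2^(−7.36/6) = 0.427 progression-free, so mS = 0.288 and mP = 0.573 if progression alone ends collection. With equal observed means of 6 (assumed):
- Minimum run: 4.27 − 2.56 = +1.7
- Maximum run: (4.27 + 2.88) − (2.56 + 5.73) = −1.1
- Possible range: 4.27 − 8.29 = −4.0 to 7.15 − 2.56 = +4.6

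The possible range is about three times as wide as the gap between the planned runs (8.6 against 2.8).

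**Week 12, same assumptions.** The shares are 0.880 and 0.727. The minimum run gives 6 × (0.880 − 0.727) = +0.9, and the maximum run gives 0.92 − 10 × 0.153 = −0.6. The possible range is 5.28 − 7.09 = −1.8 to 6.48 − 4.36 = +2.1.

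**The case against.** A reader might go further and infer that the planned runs can show nothing about how missing data move the arm difference. The documents do not support that. The missingness expected here is unequal, and then the runs do move: at Week 32 they swing 2.8 points and change sign, which would alert anyone. Exact agreement needs equal missing fractions and equal extremes.

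The plan also compares every output, not just these two runs. In the balanced example the available-data difference of 1.0 would stand beside 0.7 and 0.7. The standardized effect would fall further, because single-value imputation inflates the spread. Assuming a within-arm SD of 2, it drops from 0.50 to about 0.21 (minimum) and 0.29 (maximum). This would signal that missing data matter, but would not reveal a possible reversal.

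A reader might also infer that 2:1 allocation alone biases the imputed minima, since the larger arm tends to reach lower values. That does not follow. The LASA and worst-pain items are bounded at 0 and 10, and the text does not say that observed extremes are meant.

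Other fair points stand:
- The same-direction pairing is the natural reading, but it is not spelled out.
- Week 32 is the last scheduled visit and the most extreme, and an end-of-treatment assessment is also collected.
- Whether visits after treatment stops count as missing is not stated.
- Crossed extremes have a width set by the missing fractions alone and will often include zero.
- Palliation has its own rule and the longitudinal models have pattern-mixture analyses. Those models are named without identifying restrictions or arm-specific assumptions, and they do not extend to the by-visit tests.

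**Conclusion.** The concern holds in this form: the minimum and maximum runs do not bound the arm difference, and the by-visit t-tests and ANCOVAs have no analysis in which missing outcomes are allowed to differ adversely between arms. On a 0-10 item the possible range is −2.3 to +3.7 where both planned runs give +0.7, and −4.0 to +4.6 where they give +1.7 and −1.1.

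These sizes are illustrations. They rest on assumed observed means and missing fractions, on scale extremes of 0 and 10, on unadjusted mean differences and, for Week 32, on exponential PFS with progression ending collection. The direction of the finding depends only on the same-direction reading of the sentence.

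The scope is the optional HO1 sub-study, mainly its by-visit comparisons. The PFS analysis is untouched. This is an inexpensive improvement worth making, not a flaw that invalidates the sub-study.

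**What to change.** Keep the planned runs, and make two changes to Section 15.3.2.

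1. Define the minimum and maximum as the ends of the item's scale, the same for both arms, and state which scheduled visits count as missing.
2. Add a delta-adjusted tipping-point analysis for worst pain and overall LASA at each visit. Impute missing scores under a stated model, then shift the imputed sorafenib values unfavourably (upward for pain, downward for LASA) in steps until the conclusion changes. Report that shift in scale points, so that readers can judge whether it is plausible.

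Optionally, report the two crossed runs (sorafenib minimum with placebo maximum, and the reverse), labelled as outer bounds only.

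The cost is a short SAP edit and a few more program runs, with no new data. The downside is that the reported ranges will look less reassuring.
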